5.2. Schematic study design

Screening assessments are performed subsequent to the patient providing an informed consent and within 28 days before the first administration of SL-901 at the Run-in PK sampling day, unless otherwise specified.

In both study parts a treatment cycle is considered to be 28 days, with daily dosing throughout the cycle.

All patients will receive SL-901 as a single agent in an open-label fashion; study drug will be dispensed to patients at scheduled study center visits on a per-cycle basis. SL-901 capsules (20 mg and 60 mg) are packaged into 50-cc high-density polyethylene (HDPE) bottles, 14 capsules per bottle.

Tumor assessment will occur at Screening (for identification of baseline disease) and every 2 cycles of treatment thereafter. Response will be evaluated using Response Evaluation Criteria in Solid Tumors (RECIST) v1.1.

[figure not shown]
In Part 1a, a serially sampled PK profile will be obtained for a single dose (Run-in PK sampling) and at steady-state (C1D15); in Part 1b, the PK sample collection schedule will be informed by data collected in Part 1a.

[figure not shown]
All Serious Adverse Events (SAEs) and non-SAEs will be recorded in the study's clinical database from the day of informed consent signature (SAEs) or from the day of first exposure to SL-901 (AEs) through 30 days after the last dose of SL-901.

[figure not shown]
After completion of the End of Treatment (EOT) visit, patients will then be followed every 90 days for survival status for 12 months. The survival follow-up may be by telephone contact. If the patient discontinued study drug for reasons other than progressive disease, disease assessments should continue to be performed on an every 8-week basis (± 1 week) through 6 months after the first study drug dose and then on an every 90-day basis or until, in the judgment of the Investigator, there is evidence of relapsed or progressive disease.

[figure not shown]

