7.3. Analysis populations

The following analysis populations will be considered in the statistical analysis:

- DLT population: All patients receiving the complete run-in dose and at least 75% of the planned SL-901 doses in Cycle 1 and completing study assessments through C2D1, or patients discontinuing Cycle 1 due to DLT irrespective of the SL-901 dose actually received.
- Safety population: all patients enrolled into the study and who received any amount of SL-901.
- Efficacy population: all patients enrolled into the study and who received any amount of SL-901 (it corresponds to the safety population).
- Per Protocol (PP) population: all patients who received at least 1 cycle of treatment, have at least 1 post-baseline efficacy assessment, and have no major protocol violations.
- PK population: all patients who receive at least one dose of SL-901 and have at least one PK sample collected and the corresponding PK concentration. .

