11.5.10. Treatment exposure and compliance

The following parameters will be summarized using descriptive statistics:

- Cumulative dose (mg) is the sum of the number of capsules taken at each occasion multiplied by the strength of each capsule.
- Treatment duration from first intake (days) is calculated as (Last dose date – First dose date in run-in period + 1).
- Treatment duration from Cycle 1 Day 1 (days) is calculated as (Last dose date – First dose date in Cycle 1 Day 1 + 1).
- Actual Dose Intensity (mg/day) = [cumulative dose (mg)] / [treatment duration from first intake (days)]
- Planned Dose Intensity (mg/day) = Total daily dose for the cohort (see Table 1).
- Relative Dose Intensity (%) = [actual dose intensity (mg/day)] / [planned dose intensity (mg/day)]

Study treatment administration at the site and study drug accountability as collected in the eCRF, as well as the daily records from the patient diary will be listed.

12. Efficacy evaluations

Efficacy evaluations are based upon the Investigator's assessment.

Tumor assessment will occur at Screening (for identification of baseline disease) and after every 2 cycles of treatment thereafter. Response will be evaluated using Response Evaluation Criteria in Solid Tumors (RECIST) v1.1.

After completion of the EOT visit, patients will then be followed every 90 days for survival status for 12 months. The survival follow-up may be by telephone contact. If the patient discontinued study drug for reasons other than progressive disease, disease assessments should continue to be performed on an every 8-week basis (± 1 week) through 6 months after the first study drug dose and then on an every 90-day basis or until, in the judgment of the Investigator, there is evidence of relapsed or progressive disease.

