12.1.3. Progression-free survival

Progression-free survival (PFS) is defined as the time (in months) from the date of first intake of SL-901 to the date of the first documentation of PD (per RECIST v1.1) or death due to any cause, whichever occurs first, regardless of whether the patients withdraws from study treatment.

PFS will be analyzed by cohort and overall using the Kaplan-Meier method, with the median, 25th and 75th percentiles as well as PFS rates at 3, 6 and 12 months (and every 6 months thereafter until the end of follow-up or no more subjects are at risk) reported along with the 2-sided 95% CIs calculated according to Brookmeyer and Crowley using a linear transformation (CONFTYPE=LINEAR in SAS Proc LIFETEST). Number and percentage of patients with each event type (PD or death) and censoring reasons will be presented by cohort.

PFS will be displayed graphically using Kaplan-Meier curves.

These analyses will be presented by cohort both in the Efficacy and in the Per Protocol populations.

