12.1.4. Overall Survival

Overall survival (OS) is defined as the time from the date of first SL-901 intake to the date of death due to any cause, regardless of whether the patient withdraws from study treatment or receives another anticancer therapy.

OS (months) = [date of death or censoring – date of first SL-901 intake +1]/30.4375

Patients not known to have died at the time of analysis will be censored at the last recorded date on which the subject was known to be alive, based on the data collected in the “Long Term Follow-up” eCRF.

OS will be analyzed by cohort and overall using the Kaplan-Meier method, with the median, 25th and 75th percentiles as well as OS rates at 12, 18 and 24 months (and every 6 months thereafter until the end of follow-up or no more subjects are at risk) reported along with the 2-sided 95% CIs calculated according to Brookmeyer and Crowley using a linear transformation (CONFTYPE=LINEAR in SAS Proc LIFETEST). Number and percentage of patients with event (death) and censored will be presented by cohort and overall.

[figure not shown]
OS will be displayed graphically using Kaplan-Meier curves.

[figure not shown]
These analyses will be presented by cohort both in the Efficacy and in the Per Protocol populations.

[figure not shown]

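### The Per Protocol set is defined by events after first dose, but PFS and OS in it are timed from first dose, so PP overall survival and early PFS rates are biased upward (minor).

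*SAP*

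**What the plan says.** SAP 7.3 sets three conditions for the PP set: "all patients who received at least 1 cycle of treatment, have at least 1 post-baseline efficacy assessment, and have no major protocol violations". The first two can be met only after dosing has begun. Protocol 9.2 gives the same definition but makes a PP efficacy analysis optional, depending on the data. The comparison set has no such condition: "Efficacy population: all patients enrolled into the study and who received any amount of SL-901".

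On timing, SAP 5.2 states that "a treatment cycle is considered to be 28 days, with daily dosing throughout the cycle". The opening text of SAP section 12 places tumor assessments at Screening and "after every 2 cycles of treatment thereafter". Protocol Table 8 puts the Part 1a run-in dose 3 to 7 days before Cycle 1 Day 1.

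SAP 12.1.3 and 12.1.4 start the PFS and OS clocks at first SL-901 intake, which in Part 1a is the run-in dose. Both sections close with the same sentence: "These analyses will be presented by cohort both in the Efficacy and in the Per Protocol populations". For OS, the SAP adds that "OS will be analyzed by cohort and overall using the Kaplan-Meier method". The visible text does not move time zero for the PP set, does not use delayed entry, and does not call the PP results supportive. SAP 3.1, which lists changes from the protocol, mentions only the DLT population.

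**The concern.** Membership of the PP set depends on events that follow time zero. A patient who dies in the first cycle, or before any post-baseline scan, cannot belong to it. Every patient who does belong is known to have been alive through the qualifying interval, yet that interval counts as follow-up from first dose. This is immortal (guarantee) time. Until patients begin to qualify, the PP OS curve cannot fall, whatever the drug does.

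PFS and OS are listed secondary clinical activity endpoints (SAP 5.4.2). If the two sets are shown side by side without a caveat, a reader may take the better PP curve as the result in patients who were treated properly. Part of the difference would come only from how the set was built.

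**Working it through.** The plan states no survival assumption, event count or power, so there is no figure of its own to reproduce. The check has three parts.

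**1. Length of the guaranteed period, from first intake.** I read the first PP condition as a completed 28-day cycle.
- One-cycle rule only (an early unscheduled scan qualifies): 28 + 3 = 31 to 28 + 7 = 35 days. At 30.4375 days per month (SAP 7.2.1) this is 1.02 to 1.15 months.
- First scheduled scan, after two cycles: 56 + 3 = 59 to 56 + 7 = 63 days, or 1.94 to 2.07 months.

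**2. Overall survival.** Assume exponential OS with median m, so S(t) = exp(-t ln 2 / m). The documents give no median, so m runs from 4 to 12 months. With t0 the guaranteed period:
- share removed by early death = 1 - S(t0)
- PP survival at t ≥ t0 = S(t) / S(t0)
- PP median = m + t0, provided t0 is shorter than that median, which holds throughout

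For m = 6 and t0 = 59 days: 1 - S(t0) = 20.1%; PP median = 6 + 1.94 = 7.94 months; PP 12-month OS = 0.250 / 0.799 = 31.3%.

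| True median (months) | Removed, day 59-63 | PP median (months) | 12-month OS, all treated | 12-month OS, PP, day 59-63 | 12-month OS, PP, day 31-35 |
|---|---|---|---|---|---|
| 4 | 28.5-30.1% | 5.9-6.1 | 12.5% | 17.5-17.9% | 14.9-15.3% |
| 6 | 20.1-21.3% | 7.9-8.1 | 25.0% | 31.3-31.8% | 28.1-28.6% |
| 9 | 13.9-14.7% | 10.9-11.1 | 39.7% | 46.1-46.5% | 42.9-43.4% |
| 12 | 10.6-11.3% | 13.9-14.1 | 50.0% | 55.9-56.3% | 53.0-53.4% |

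The 12-month gain is about 5 to 7 points at the scheduled scan, and about 2 to 4 points if only the one-cycle rule binds. Under the one-cycle rule the median still shifts by 1.0 to 1.15 months.

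**3. Progression-free survival.** This was simulated with 20,000 patients per scenario. Scans fall at day 59 and every 56 days after. PD is dated at the scan that detects it, and death is an event at any time. PP means alive and scanned at day 59. Either 0% or 10% leave alive without a scan; in the Efficacy set these are censored at the start, in line with SAP 11.3.

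| Assumed OS / progression median (months) | Leave without scan | Median PFS, Efficacy → PP (months) | 3-month PFS, Efficacy → PP |
|---|---|---|---|
| 4 / 2 | 0% | 1.94 → 2.04 | 30.6% → 42.6% |
| 4 / 2 | 10% | 1.94 → 2.10 | 29.7% → 42.4% |
| 6 / 2 | 0% | 1.94 → 2.10 | 35.8% → 44.6% |
| 6 / 2 | 10% | 1.94 → 2.10 | 35.1% → 44.5% |
| 6 / 4 | 0% | 3.12 → 3.78 | 50.7% → 63.3% |
| 6 / 4 | 10% | 3.02 → 3.78 | 50.2% → 63.7% |
| 9 / 4 | 0% | 3.78 → 3.78 | 57.0% → 65.4% |
| 9 / 4 | 10% | 3.78 → 3.78 | 55.2% → 64.9% |

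The median moves by 0 to about 0.8 months. 3-month PFS rises by 8.4 points (65.4 - 57.0) to 13.5 points (63.7 - 50.2).

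**Small-cohort illustration.** In a cohort of three, one death at day 40 before any scan takes the Efficacy OS curve to 2/3 = 67%. The PP curve, now based on two patients, stays at 100%.

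**The case against.** The strongest reply is that the analysis without this bias is already in the plan. PFS and OS are reported for all treated patients, and the protocol makes the PP analysis optional. Clinical activity is a secondary objective. There is no comparator, no hypothesis test and no formal sample size; the MTD rests on DLTs. The study stopped early and Part 1b never opened (SAP section 4). All of this stands, and it limits the point to a display problem.

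A second reply is that Part 1a cohorts have 3 to 6 patients. One death moves an uncensored Kaplan-Meier curve by 17 to 33 points, so a 6-point average shift cannot be seen within a cohort. That is fair for any single cohort. The shift matters more in a pooled curve, and SAP 12.1.4 does call for an overall OS analysis, although its closing sentence on populations mentions presentation by cohort only. In a small cohort the bias appears as a whole early death going missing, as in the illustration above.

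A third reply is that PFS differs from OS. A patient whose first scan shows PD can still enter the PP set and counts as an event. A patient who leaves alive without a scan is censored at first dose in the Efficacy set and adds almost nothing there. This also stands, and it is why the PFS median moves so little. It does not remove the gain in early PFS rates.

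Two stronger inferences are tempting. One is that the PP result must look better than the Efficacy result in every case. The documents do not support that: PP status also depends on major protocol violations, judged case by case (SAP 7.4.2), and those exclusions can act in either direction. With no early death, the two sets may coincide. The other is that the trial's activity conclusions or dose decisions are compromised. Nothing in the plan makes either depend on PP survival.

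**Conclusion.** The point holds as a minor one. With the PP set defined as it is and the clock started at first intake, PP OS is biased upward, and so are early PFS rates. The direction follows from the definitions alone. The size rests on assumed exponential medians that the documents do not give, on reading the one-cycle condition as a completed cycle, and on taking an efficacy assessment to mean a tumor assessment.

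A scheduled first scan adds about 2 months to median OS and 5 to 7 points to 12-month OS. If an early unscheduled scan qualifies, the figures are about 1 month and 2 to 4 points. For PFS the main effect is on early rates and not on the median. PFS censoring detail may lie in figures that are not shown, but it would not undo selection on survival. The Efficacy-population results are unaffected.

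**What to change.** In SAP 12.1.3 and 12.1.4, change the closing sentence so that PFS and OS are reported in the Efficacy population only.

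If a PP display of OS is kept, start its clock at the qualifying assessment, or use delayed entry at that time. Label it supportive and conditional on surviving to that assessment. Do not use a landmark for PFS unless it is limited to patients who are progression-free at the landmark; otherwise PD found on the qualifying scan falls at time zero.

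In SAP 12.1.1, label PP response and disease control rates as supportive too, because early deaths leave their denominator. If 20.1% are removed and none of them responded, PP ORR is inflated by a factor of 1 / 0.799 = 1.25.

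The cost is two edited sentences, one added label, and the loss of one supportive display for each endpoint. No result in the all-treated population changes.

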7.4. On study and pre-study closure activities

7.4.1. Data monitoring

This study will be monitored in accordance with the ICH Guidelines for GCP.

In conjunction with the investigators, the Sponsor will constantly monitor the incoming safety data, especially TEAEs, SAEs and SUSARs to continuously assess the overall risk/benefit of the patients enrolled in this study and to take appropriate actions.

The DM review is also intended as data quality check in order to verify the consistency of the data entered and identify any possible misconduct from the site.

All monitoring activities will be described in detail in the study-specific monitoring plan.

Data Safety Review Committee

Weekly cohort review meetings and dose escalation meetings were regularly conducted during Part 1 to closely monitor the patients' safety.

7.4.2. Protocol Deviations and Data Review Meeting

Critical, Major or minor protocol deviations are defined based on the impact on the efficacy or safety of study treatments.

Before database lock, a data review meeting (DRM) will take place to identify protocol deviations. Major protocol violations will be discussed, and on a case-by-case basis it will be determined whether or not to exclude the patients from the Per Protocol population. The final decisions on which patients to include or exclude from the Per Protocol population will be finalized prior to database lock.

Categories of protocol violations will be defined and will be integrated in the statistical analysis.

Significant protocol violations that potentially compromise the data integrity and patients' safety will be summarized on the Safety Population as follows:

- The number and percentage of patients with a critical protocol deviation by cohort and overall and by type of deviation
- The number and percentage of patients with a major protocol deviation by cohort and overall and by type of deviation
- The number and percentage of patients with a minor protocol deviation by cohort and overall and by type of deviation
 - A by-patient listing of all critical protocol deviations.
 - A by-patient listing of all major protocol deviations.
 - A by-patient listing of all minor protocol deviations.

8. Determination of sample size

No formal sample size calculation is required in this Phase 1 dose-escalation and dose expansion study. For each dosing schedule, 3 to 6 patients are to be enrolled in each dose escalation cohort in Part 1a. Up to 60 patients in total are to be enrolled in the dose escalation cohorts.

The total number of patients to be enrolled is dependent upon the observed safety profile, which will determine the number of patients per dose cohort, as well as the number of dose-escalations required to achieve the MTD.

A sample size of at least 3 patients in each cohort, expanding to 6 patients in the event of a marginal DLT rate (33%), is a conventional approach in dose-escalation studies of investigational oncologic agents.

Six to 12 patients in each expansion cohort (up to 4 cohorts) are to be enrolled in Part 1b.

9. Randomization Methodology

Not applicable.

10. Stopping Rules and Blinding

10.1. Stopping Rules

Not applicable.

10.2. Blinding

This is an open-label study; thus, study subjects and investigators will not be blinded to treatment assignment.

Unblinded safety data will be reviewed at all dose-escalation steps by the DSRC.

11. Statistical analysis and methods

11.1. Multiplicity adjustment

Not applicable.

11.2. Descriptive statistics

All study variables (with the exception of PK variables) will be presented by cohort and overall separately for each study part, using the appropriate descriptive statistics according to the variable nature, unless otherwise specified:

- **Continuous variables:** number of non-missing observations, arithmetic mean, standard deviation (SD), minimum, median, maximum;
- **Categorical variables:** number of non-missing observations and column percentages (n, %), where percentage is calculated over the relative population; when tabulating categorical data, “missing” will be included as a category and the number of subjects with missing data will be presented.
- **Time to event variables:** number of non-missing observations, number and percentage of events, number and percentage of censored observations, 1st quartile (Q1), median and its 95% Confidence Interval (CI), 3rd quartile (Q3), Kaplan-Meier survival curves.

The behaviour over time of study variables will be summarised by cohort and overall as follows:

- **Continuous variables:** descriptive statistics for each assessment time point;
- **Categorical variables:** descriptive statistics for each assessment time point.

11.3. Data imputation

Adverse Events

Completely missing AE dates (i.e., missing day, missing month and missing year) will not be imputed. Partial AE start and stop dates will be imputed according to the rules as follows in a sequential fashion.

In the imputation of missing or partial dates, if the imputed date is after min (death date, cut-off date), min (death date, cut-off date) will be used as the imputed date.

AE Stop Date

- If month and year are present, then impute as the last day of that month
- If only the year is present, impute as December 31 of that year
- If the stop date is entirely missing, assume the event is ongoing

AE Start Date

- If month and year are present, and are not equal to the month and year of the first dose, then imputed as the first day of the month
- If month and year are present, and are equal to the month and year of first dose
 - If stop date is complete and earlier than the date of first dose, then impute as the first day of the month
 - Else impute as the date of first dose
- If only the year is present, and the year is not equal to the year of the first dose, then impute as January 1 of the year
- If only the year is present, and the year is equal to the year of the first dose
 - If stop date is complete and earlier than the date of first dose, then impute as January 1 of the year
 - If stop date is partially missing and the month and year of stop date are earlier than the month and year of first dose, then impute as January 1 of the year
 - Else impute as the date of first dose
- If the start date is entirely missing
 - If the stop date is complete and earlier than the date of first dose, then impute as January 1 of the stop year
 - If the day of stop date is missing, and the month and year are earlier than the month and year of first dose, then impute as January 1 of the stop year
 - If the day and month of stop date are missing, and the year is earlier than the year of first dose, then impute as January 1 of the stop year
 - Else impute as the date of first dose

Prior and Concomitant Medications

The same imputation rules as outlined for the Adverse Events will be used for Prior and Concomitant Medications.

Post-treatment systemic anti-cancer therapy

- In case of partial start date of post-treatment systemic anti-cancer therapy, the date will be imputed as the first day of the month but not earlier than the last dose date.
- In case of completely missing start date, it will be imputed as:
min [max(PD date + 1, last SL-901 dose date + 1), end date of new anti-cancer therapy].

Last study drug administration

The following rules should be used for the imputation of date of last SL-901 administration:

- If the date of last administration is completely missing and there is no EOT eCRF and no death date, the subject is considered as ongoing and the cut-off date should be used as the last dosing date.
- If the date of last administration is completely or partially missing and the EOT eCRF is available (prior to any death date or withdrawal of consent date, if available):
 - Case 1: The date of last administration is completely missing, and the EOT visit date is complete, then this latter date should be used.
 - Case 2: Only Year(yyyy) of the dose end date is available and yyyy < the year of EOT date:
Use Dec31yyyy
 - Case 3: Only Year(yyyy) of the dose end date is available and yyyy = the year of EOT date:
Use EOT date
 - Case 4: Both Year(yyyy) and Month (mm) are available for the date of last administration, and yyyy = the year of EOT date and mm < the month of EOT visit: Use the last day of the Month (mm).
 - Use min (EOT date, death date) for all other cases.

After imputation, compare the imputed date with the start date of that specific record, if the imputed date is < start date of that record: Use the start date of that record.

Tumor Assessment

Completely or partially missing Tumor Assessment (TA) dates will not be imputed.

- In case date of last TA is missing and there are no previous TA dates, then the date of first study drug admin will be used for censoring

- In case date of last TA is missing and there are previous TA dates, then the previous TA date will be used for censoring
- If there are multiple scan dates associated with an evaluation, the earliest of the scan dates associated with the evaluation will be used as the date of assessment.

Handling of PK concentrations Below the Lower Limit of Quantification and missing sampling timepoints

In all data presentations (except listings), plasma concentration values below the lower limit of quantification (BLQ) will be set to zero before the t_{max} and to “missing” after the t_{max} . Data-replacements will be implemented by the PK analyst from Clinical Pharmacology and Pharmacometrics department.

In listings, BLQ values will be reported as “BLQ”.

A footnote will be added to the listing, tables, and figures, to indicate the lower limit of quantification (LOQ) value.

If more than half of the subjects in a given analyte/time point combination have values <BLQ, then the descriptive statistics will not be presented and instead displayed as BLQ for the mean and missing for all other statistics.

If actual sampling time is missing, the nominal time will be used and flagged in the listings.

